 - In a clinical trial with another TNF-antagonist worsening congestive heart failure and increased mortality due to congestive heart failure have been observed. Cases of worsening congestive heart failure have also been reported in patients receiving Humira.
- Autoimmune processes
 - Treatment with Humira may result in the formation of autoimmune antibodies. The impact of long term treatment with Humira on the development of autoimmune diseases is unknown.
- Concurrent administration of biologic DMARDS or TNF-antagonists
 - Concomitant administration of adalimumab with other biologic DMARDS (e.g., anakinra and abatacept) or other TNF-antagonists is not recommended based upon the possible increased risk for infections, including serious infections and other potential pharmacological interactions.
- Elderly patients
 - The frequency of serious infections among Humira treated subjects over 65 years of age (3.6%) was higher than for those under 65 years of age (1.4%).

- Some of those had a fatal outcome. Particular attention regarding the risk for infection should be paid when treating the elderly.
- Surgery
 - There is limited safety experience of surgical procedures in patients treated with Humira.

The SmPC states that the long half-life of adalimumab should be taken into consideration if a surgical procedure is planned. A patient who requires surgery while on Humira should be closely monitored for infections, and appropriate actions should be taken.

The study will be conducted in subjects previously treated with MTX for PsA at 15 mg ew for at least 4 weeks. Thus, enrolled subjects will have already been exposed to MTX. For subjects randomized into the MTX escalation arm, a dose increase up to 20-25 mg ew will be required, which is the highest recommended dose in PsA^{11,27} and also approved dose for PsA.³⁸ Rapid MTX dose escalation in subjects with PsA up to 25 mg ew has been studied before, though with a different research objective. The majority, 91% and 83% of patients were able to reach the MTX dose of at least 20 and 25 mg ew, respectively, with no major safety issue.^{18,27} Further, in the present study subjects are allowed to de-escalate to the highest tolerable MTX dose in the case of suspected MTX toxicity or intolerance.

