5.4 Removal of Subjects from Therapy or Assessment

5.4.1 Discontinuation of Individual Subjects

A subject may withdraw from the study at any time. The Investigator may discontinue any subject's participation for any reason, including an adverse event, safety concerns or failure to comply with the protocol.

Subjects will be withdrawn from the study if any of the following occur:

- Clinically significant abnormal laboratory result(s) or adverse event(s), as determined by the Investigator in consultation with the AbbVie TA MD.
- The Investigator believes it is in the best interest of the subject.
- The subject requests withdrawal from the study.
- Inclusion and exclusion criteria violation was noted after the subject started study drug, when continuation of the study drug would place the subject at risk as determined by the AbbVie TA MD.
- Introduction of prohibited medications or dosages when continuation of the study drug would place the subject at risk as determined by the AbbVie TA MD.
- Joint surgery
- The subject becomes pregnant while on study medication.
- Subject has known dysplasia of the gastrointestinal tract or malignancy, except for localized non-melanoma skin cancer. Discontinuation for carcinoma in-situ of the cervix is at the discretion of the Investigator.
- Subject is diagnosed with lupus like syndrome, multiple sclerosis or demyelinating disease.
- Subject is non-compliant with TB prophylaxis.
- The subject develops tuberculosis, or any other significant or opportunistic infections.
- Subject is significantly non-compliant with study procedures which would put the subject at risk for continued participation in the trial in consultation with the AbbVie TA MD.

If, during the course of study drug administration, the subject prematurely discontinues study drug use, the procedures outlined for the PD visit must be completed within 2 weeks of the last dose of study drug, and preferably prior to the initiation of another therapy. However, these procedures should not interfere with the initiation of any new treatments or therapeutic modalities that the Investigator feels are necessary to treat the subject's condition. Following discontinuation of the study drug, the subject will be treated in accordance with the Investigator's best clinical judgment.

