6.1.1.2 Serious Adverse Events

If an adverse event meets any of the following criteria, it is to be reported to AbbVie as a serious adverse event (SAE) within 24 hours of the site being made aware of the serious adverse event.

Death of Subject	An event that results in the death of a subject.
Life-Threatening	An event that, in the opinion of the investigator, would have resulted in immediate fatality if medical intervention had not been taken. This does not include an event that would have been fatal if it had occurred in a more severe form.
Hospitalization or Prolongation of Hospitalization	An event that results in an admission to the hospital for any length of time or prolongs the subject's hospital stay. This does not include an emergency room visit or admission to an outpatient facility.
Congenital Anomaly	An anomaly detected at or after birth, or any anomaly that results in fetal loss.
Persistent or Significant Disability/Incapacity	An event that results in a condition that substantially interferes with the activities of daily living of a study subject. Disability is not intended to include experiences of relatively minor medical significance such as headache, nausea, vomiting, diarrhea, influenza, and accidental trauma (e.g., sprained ankle).

Important Medical Event Requiring Medical or Surgical Intervention to Prevent Serious Outcome

An important medical event that may not be immediately life-threatening or result in death or hospitalization, but based on medical judgment may jeopardize the subject and may require medical or surgical intervention to prevent any of the outcomes listed above (i.e., death of subject, life-threatening, hospitalization, prolongation of hospitalization, congenital anomaly, or persistent or significant disability/incapacity). Additionally, any elective or spontaneous abortion or stillbirth is considered an important medical event. Examples of such events include allergic bronchospasm requiring intensive treatment in an emergency room or at home, blood dyscrasias or convulsions that do not result in inpatient hospitalization, or the development of drug dependency or drug abuse.

For serious adverse events with the outcome of death, the date and cause of death will be recorded on the appropriate case report form.

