6.1.7 Toxicity Management

Adalimumab

Subjects who develop a new infection while undergoing treatment with adalimumab should be monitored closely. Administration of study injections should be interrupted if a subject develops an infection requiring IV anti-infective treatment or if an infection meets the definition of "serious" (see Section 6.0 for definitions). Study medication may be restarted once the physician determines that the infection has been successfully treated. Otherwise prohibited concomitant medications may be given if medically necessary.

Prior to use, every attempt should be made to contact the AbbVie Study Physician for direction on re-introduction of adalimumab therapy after prohibited medication administration.

If the subject must undergo elective surgery, the study injections must be interrupted 2 weeks prior to the surgery. If the subject must undergo emergency surgery, the study injections must be interrupted at the time of the surgery. The injectable study medication can recommence at least 2 weeks after surgery once the physician has examined the surgical site and determined that it has healed and there is no sign of infection.

Methotrexate

The definition of MTX intolerance and/or toxicity is based on MTX intolerance and toxicity as described in the MTX prescribing information provided to the investigator. An event of intolerance or toxicity is to be recorded as AE. The decision for treatment adjustment is at the investigator's discretion.

MTX will be escalated by 5.0 mg every 2 weeks. If MTX intolerance/toxicity is suspected, MTX dose reduction by 5 mg, including during the escalation period, may be performed. Any subject who cannot tolerate the highest recommended dose specified in the protocol (20-25 mg ew) due to toxicity or intolerance, is permitted to continue on the highest tolerable dose.

Temporary MTX discontinuation followed by re-introduction/re-escalation of MTX is allowed if the issue resolves within 4 weeks. The TA MD must be consulted if the Investigator would like to temporarily discontinue MTX more than one time.

If the investigator would like to decrease the MTX dose for any reasons other than MTX intolerance/toxicity, the AbbVie TA MD must be contacted first.

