7.0 Protocol Deviations

AbbVie does not allow intentional/prospective deviations from the protocol unless when necessary to eliminate an immediate hazard to study subjects. The principal investigator is responsible for complying with all protocol requirements, and applicable global and local laws regarding protocol deviations. If a protocol deviation occurs (or is identified) after a subject has been enrolled, the principal investigator is responsible for notifying Independent Ethics Committee (IEC)/Independent Review Board (IRB) regulatory authorities (as applicable), and the following AbbVie Clinical Contacts:

Primary Contact:

[name]
[name]
USA

Office:

Fax:

Alternate Contact:

[name]
France

Office:

Fax:

Such contact must be made as soon as possible to permit a review by AbbVie to determine the impact of the deviation on the subject and/or the study.

For the purposes of this protocol, reportable deviations are defined as:

- Subject entered into the study even though she/he did not satisfy entry criteria
- Subject who developed withdrawal criteria during the study and was not withdrawn

- Subject who received wrong treatment or incorrect dose
- Subject who received excluded or prohibited concomitant treatment

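### Protocol 5.4.1 requires withdrawal for tuberculosis or an opportunistic infection, but 6.1.7 permits adalimumab restart after serious or IV-treated infections without excepting either

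*Protocol*

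**What the plan says.** Protocol Section 5.4.1 opens its list with "Subjects will be withdrawn from the study if any of the following occur". One entry reads "The subject develops tuberculosis, or any other significant or opportunistic infections". Some entries in that list are qualified by the investigator's judgement or by consultation with the sponsor's medical director. The infection entry has no such qualifier, and *significant* is not defined in either document.

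Protocol Section 6.1.7 treats infection under the heading for adalimumab. It begins "Subjects who develop a new infection while undergoing treatment with adalimumab should be monitored closely" and continues "Administration of study injections should be interrupted if a subject develops an infection requiring IV anti-infective treatment or if an infection meets the definition of" (the term that completes the sentence is *serious*). It then adds "Study medication may be restarted once the physician determines that the infection has been successfully treated". Section 6.1.1.2 defines *serious*; one of its criteria is "An event that results in an admission to the hospital for any length of time or prolongs the subject's hospital stay". The methotrexate part of 6.1.7 has no rule specific to infection.

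Section 7.0 lists as a reportable deviation: "Subject who developed withdrawal criteria during the study and was not withdrawn".

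On scoring, Protocol 8.1.2 counts a subject who discontinues in Part 1 with missing data as a non-responder. SAP 4.7 counts a subject who discontinues prematurely as a non-responder at all later visits.

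**The concern.** Two current sections can apply to the same event. One ends the subject's participation. The other lets the subject resume a TNF inhibitor. Protocol Section 3.4 lists active tuberculosis, other severe infections and opportunistic infections as contraindications to adalimumab, so what a site does about re-exposure should not depend on which section it opens.

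There are two further consequences. A site that relies on 6.1.7 may commit a reportable deviation without realising it. The choice can also decide how a subject is scored. A subject withdrawn before Week 16 is an MDA non-responder and does not enter Part 2, whereas a subject who restarts keeps the observed Week 16 result and goes on. The trial is open-label, so the choice is made with treatment known.

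**Working it through.** **Step 1. The two rules by type of event**

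| Event in a subject on adalimumab | Section 5.4.1 | Section 6.1.7 |
|---|---|---|
| Tuberculosis or opportunistic infection that is serious or IV-treated | Withdraw | Interrupt; restart permitted after successful treatment |
| Other serious or IV-treated infection | Withdraw if *significant* (undefined) | Interrupt; restart permitted after successful treatment |

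In the first row both triggers are met on their own words, so no interpretation is needed. In the second row the answer turns on whether a serious infection is also *significant*. Ordinary usage suggests that a hospitalised infection would be, but the documents do not say so.

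**Step 2. Arms.** The interrupt-and-restart text is written for subjects on adalimumab. In Part 1, subjects on methotrexate alone have only the 5.4.1 rule for infection. Handling could therefore differ by arm.

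**Step 3. The plan's own power figure.** Protocol 8.2 and SAP 4.4 give 40% versus 20%, 120 per arm, two-sided 0.05, about 10% dropout and at least 90% power. The check uses an unstratified normal approximation with pooled variance under the null:

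power = Φ{[(p1 − p2) − 1.96·√(2·p̄(1 − p̄)/n)] / √[(p1(1 − p1) + p2(1 − p2))/n]}, where p̄ is the mean of p1 and p2.

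- n = 120: (0.20 − 1.96 × 0.0592)/0.0577 = 1.456, power 92.7%.
- n = 108 (120 less 10%): (0.20 − 1.96 × 0.0624)/0.0609 = 1.278, power 89.9%.

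The stated figure is reproduced to within rounding. The point does not depend on it.

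**Step 4. Size of the endpoint effect.** The only infection frequencies in the documents are in Protocol 3.4: serious infections in 1.4% of adalimumab-treated subjects under 65 and 3.6% of those over 65, with no exposure period given. Assume that these apply to the adalimumab arm during Part 1, that each case would be withdrawn under one reading and restarted under the other, and that 40% would otherwise have been in MDA.

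- One would-be responder lost: 1/120 = 0.83 points.
- At 1.4%: 120 × 0.014 = 1.68 cases; × 0.40 = 0.67 responders; 0.67/120 = 0.56 points. The MDA rate falls from 40% to 39.44%.
- At 3.6%: 120 × 0.036 = 4.32 cases; × 0.40 = 1.73 responders; 1.73/120 = 1.44 points. The MDA rate falls from 40% to 38.56%.

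With the methotrexate arm held at 20% and 120 per arm, the Step 3 formula gives power of 91.4% and 89.0%, against 92.7%.

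**The case against.** The strongest reply is that the two sections can be obeyed together. Restart is permitted, not required, so a site can interrupt under 6.1.7 and withdraw under 5.4.1 without breaching either. On that view 6.1.7 is the general rule and 5.4.1 a narrower bar on restart. There are also safeguards. A physician must judge the infection successfully treated, serious events reach the sponsor within 24 hours, and 5.4.1 separately covers withdrawal for clinically significant adverse events in consultation with the sponsor's medical director.

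Part of this stands: the defect is a missing exception and an undefined word, not two commands that cannot both be carried out. But nothing in the protocol ranks the sections. Section 5.3.1.1 points sites to 6.1.7 for toxicity management without mentioning 5.4.1. The sponsor contact on re-introduction in 6.1.7 is tied to use of prohibited medication, not to infection alone. A site that uses the permission 6.1.7 gives, after tuberculosis or an opportunistic infection, is in deviation under 7.0.

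A reader might infer four stronger points that the documents do not support:

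- *Every serious infection requires withdrawal.* Section 5.4.1 does not use the word *serious*, and neither document equates it with *significant*.
- *The two arms have contradictory infection rules, because methotrexate has a 4-week limit on temporary discontinuation.* That limit sits in the text on methotrexate intolerance and toxicity and is not written as an infection rule.
- *The adalimumab rate could move by 1.4 to 3.6 points.* That requires every affected subject to be a would-be responder.
- *Membership of the per-protocol set is altered.* That analysis is optional, major violations are settled before the final lock, and no text makes a reportable deviation a major violation.

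**Conclusion.** The inconsistency is real and should be corrected on safety grounds. It is explicit for tuberculosis or an opportunistic infection that is serious or IV-treated in a subject on adalimumab. For other serious infections it is conditional on what *significant* means. Different handling by arm is possible but not established.

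The primary comparison is barely touched: about 0.6 to 1.4 points off the adalimumab arm's MDA rate, against a planned difference of 20 points. Even that range is generous. The frequencies are general adalimumab figures with no exposure period, the upper end treats the whole arm as over 65, and all cases are assumed to occur before Week 16. They also count serious infections of all kinds, not just the tuberculosis and opportunistic cases where the conflict is explicit. Nothing here threatens the trial's power. Which clinical rule is right is outside this review.

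**What to change.** Reconcile Protocol Sections 5.4.1 and 6.1.7 into one rule that:

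- states which infections lead to withdrawal and which, if any, to interruption with possible restart;
- defines *significant* or replaces it with one defined term. *Serious* is already defined in 6.1.1.2, and SAP Appendix A already separates serious, opportunistic and tuberculosis categories;
- states which study drugs and which arms it covers, including subjects on methotrexate alone;
- cross-refers 5.4.1, 6.1.7 and 7.0, so that following the rule cannot itself be a deviation.

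The sponsor's medical lead decides the clinical content. The cost is a few lines of protocol text and a letter to sites, with no new data, visits or subjects. If any such cases have already arisen (the documents report none), the letter should say how to classify them for deviation reporting, and some may need reclassifying.

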5.4.2 Discontinuation of Entire Study

AbbVie may terminate this study prematurely, either in its entirety or at any study site, for reasonable cause provided that written notice is submitted in advance of the intended termination. The investigator may also terminate the study at his/her site for reasonable cause, after providing written notice to AbbVie in advance of the intended termination. Advance notice is not required by either party if the study is stopped due to safety concerns. If AbbVie terminates the study for safety reasons, AbbVie will immediately

notify the investigator by telephone and subsequently provide written instructions for study termination.

5.5 Treatments

5.5.1 Treatments Administered

5.5.1.1 Adalimumab

Adalimumab will be administered in this study open-label and at the standard dosing regimen 40 mg sc eow except in one arm of Part 2 as described below.

- Subjects randomized to Arm 1/Part 1 or assigned to Arms 1 and 4 of Part 2 at Week 16 (as described in Section 5.1 and Table 2), will receive adalimumab 40 mg eow. Starting at the Baseline (Day 1) visit, subjects who are eligible for randomization will receive the first dose of study drug: adalimumab 40 mg/0.8 mL.
- Subjects assigned to Arm 2/Part 2 (as described in Section 5.1 and Table 2), will receive adalimumab 40 mg ew beginning at the Week 16 visit.
- Subjects entering the rescue arm at or after Week 24 will have adalimumab introduced or escalated at the Investigator's discretion. For the recommended rescue treatment regimens see Section 5.1 Overall Study Design and Plan: Description.

5.5.1.2 Methotrexate

MTX will be administered open-label either orally as tablets or subcutaneously by pre-filled pens (sc) as outlined below.

- Subjects randomized to Arm 1/Part 1 will continue at the stable dose of MTX 15 mg ew (as described in Section 5.1 and Table 3).
- Subjects randomized to Arm 2/Part 1 will increase MTX dose to 20-25 mg or highest tolerable dose ew as described below (see also Section 5.1 and Table 3).

- Subjects assigned to Arm 1/Part 2 will discontinue MTX at Week 16 (Section 5.1 and Table 3). MTX should be discontinued immediately and completely at the Week 16 Visit (subjects will not taper-off MTX).
- Subjects assigned to Arm 2/Part 2 will continue at the stable dose of MTX 15 mg ew after the Week 16 visit (see also Section 5.1 and Table 3).
- Subjects assigned to Arm 3/Part 2 will continue MTX at 20-25 mg or highest tolerable dose ew after the Week 16 Visit (as described in Section 5.1 and Table 3).
- Subjects assigned to Arm 4/Part 2 will continue MTX at 20-25 mg or highest tolerable dose ew after the Week 16 Visit (as described in Section 5.1 and Table 3).
- Subjects entering the rescue arm at or after Week 24 will have MTX introduced or escalated at the Investigator's discretion. For the recommended rescue treatment regimens see Section 5.1 Overall Study Design and Plan: Description.

During the study subjects should remain on their regular MTX administration schedule as prior to the study and MTX should be taken on the same day and approximately the same time of day ew.

The escalation of MTX dose in Arm 2/Part 1 should be in the increments of 5 mg every two weeks until the MTX dose of 20-25 mg ew is reached.^{27,66,67} The dose escalation begins on Day 1, starting with MTX 20 mg ew as the first MTX dose at or after Day 1, as applicable according to the MTX administration schedule prior to study enrolment. The dose of MTX should only be escalated providing there are no clinical and/or laboratory signs of MTX intolerance or toxicity.

In the case of clinical and/or laboratory signs of MTX intolerance/toxicity, MTX dose may be de-escalated by 5 mg, including during the MTX escalation period.^{67,68} The subject may stay on the highest tolerable MTX dose which is lower than 20-25 mg ew if MTX intolerance/toxicity occurred, see Section 6.1.7 for additional information. MTX dose should not exceed 25 mg ew in this study.

Change in the route of MTX administration (between oral and sc) is allowed at any time as deemed necessary by the Investigator. Switching from oral to sc administration may improve MTX bioavailability and/or decrease MTX intolerance/toxicity, particularly at MTX doses ≥ 20 mg ew.⁶⁹

The tolerability of oral MTX at doses ≥ 20 mg ew may also be improved by dividing the total dose of MTX into two administrations on the same day, but not exceeding the total daily dose of MTX to be taken in the week.

All subjects receiving MTX in this study are recommended to be on folic or folinic acid supplementation with the dose and regimen chosen at the Investigator's discretion (see Section 5.2.3.1 Prior and Concomitant Therapy).

There is no required timely relationship between MTX and adalimumab administration per this protocol, but in general MTX and adalimumab are not advised to be administered on the same day.

